## 8.2 Infusion-related Toxicities and Management

Infusion reactions should be graded according to the criteria for infusion-related reaction located in the National Cancer Institute's Table for CTCAE, version 5.0, found on the National Cancer Institute Web site:

[https://ctep.cancer.gov/protocolDevelopment/electronic\\_applications/docs/CTCAE\\_v5\\_Quick\\_Reference\\_5x7.pdf](https://ctep.cancer.gov/protocolDevelopment/electronic_applications/docs/CTCAE_v5_Quick_Reference_5x7.pdf)

These reactions may manifest with signs and symptoms that may include, but are not limited to, fever, chills, headache, rash, pruritus, arthralgia, hypo- or hypertension, bronchospasm, or other symptoms. Severe infusion (Grade 3 or 4) reactions require the immediate interruption of study drug. The infusion should not be restarted and no further study medication (cemiplimab/placebo) should be given. Appropriate medical therapy including epinephrine, corticosteroids, IV antihistamines, bronchodilators, and supplemental oxygen should be available for use in the treatment of such reactions. Participants should be carefully observed until complete resolution of all signs and symptoms occurs. In each case of an infusion reaction, the site investigator should

institute treatment measures according to the best available medical practice. The core study team must be notified within 24 hours by email at [[contact]](mailto:[contact]) regarding toxicities associated with cemiplimab/placebo that result in the discontinuation of the infusion.

8.2.1 Grade 1: Mild transient reaction; infusion interruption not indicated; intervention not indicated.

For participants who develop a Grade 1 AE or toxicity during infusion, it is recommended that the study drug infusion rate be decreased by 50% and the participant should be monitored closely for any worsening of the initial signs of symptoms. If the infusion reaction recurs and/or persists at the decreased rate of infusion, the rate of the infusion may be further reduced. The maximum time of infusion should not exceed 3 hours (180 minutes). If symptoms persist but do not worsen, completion of the cemiplimab/placebo infusion will be at the discretion of the site investigator with careful monitoring.

NOTE: Blood draws for PK analysis should be timed to occur within 15 minutes after the end of the infusion.

If a participant chooses to discontinue a cemiplimab/placebo infusion, the site should notify the A5370 core study team by email at [[contact]](mailto:[contact]) and encourage the participant to complete subsequent study visits until the end of the study. Refer to [section 6.2.5](#) for discontinuation evaluation instructions.

8.2.2 Grade 2: Moderate reaction; infusion interruption indicated but participant responds promptly to symptomatic treatment (e.g., antihistamines, NSAIDS, narcotics, IV fluids); prophylactic medications indicated for ≤24 hours.

For participants who develop a Grade 2 AE or toxicity during a cemiplimab/placebo infusion, the infusion should be stopped and the core study team must be notified within 24 hours by email at [[contact]](mailto:[contact]). Administer epinephrine, corticosteroids, IV antihistamines, bronchodilators, and/or supplemental oxygen as medically indicated. At the discretion of the site investigator, the infusion may be continued at 50% of the previous infusion rate once the adverse reaction has resolved or has decreased to Grade 1 in severity. Participant must be monitored closely for any recurrence or worsening or signs or symptoms. If the infusion reaction recurs at this rate of infusion, the rate may be further reduced, again at the discretion of the site investigator. The maximum time of infusion should not exceed 3 hours (180 minutes).

Participants who develop a Grade 2 AE or toxicity during a cemiplimab/placebo infusion may complete the infusion at the discretion of the site investigator, with careful monitoring. Grade 2 AEs that may be related to cemiplimab/placebo should be handled according to standard clinical practice and documented on the eCRF.

8.2.3 Grade 3: Prolonged reaction (participant not rapidly responsive to symptomatic medication and/or brief interruption of infusion) or recurrence of symptoms following initial improvement or hospitalization indicated for clinical sequelae

DISCONTINUE further doses of cemiplimab/placebo.

Participants who develop a Grade 3 AE or toxicity during a cemiplimab/placebo infusion should have infusion discontinued immediately and be disconnected from the infusion tubing. Administer epinephrine, corticosteroids, IV antihistamines, bronchodilators, and/or supplemental oxygen as medically indicated. No further study drug treatment should be administered. The core study team must be notified within 24 hours by email at [[contact]](mailto:[contact]).

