## 9.0 CRITERIA FOR DISCONTINUATION

### 9.1 Permanent and Premature Treatment Discontinuation

Study treatment is two single infusions of cemiplimab (anti-PD-1 antibody) or placebo. Study treatment should be discontinued for:

- Drug-related toxicity (see [section 8.1](#))
- A Grade 3 or 4 infusion reaction occurs (see [section 8.2](#))
- Discontinuation of ART
- Requirement for prohibited concomitant medications (see [section 5.4](#))
- Pregnancy or breastfeeding
- Request by participant to terminate treatment
- Clinical reasons believed life-threatening by the physician, even if not addressed in [section 8.1](#) of the protocol
- Positive results for antibodies to TPO, GAD65/GAD or islet cell antigen
- An irAE of any grade occurs
- Prolonged need (>7 days) for systemic steroids

NOTE A: Participants who receive one infusion but for whom treatment was discontinued prematurely will be followed on study off treatment per the schedule of events.

NOTE B: If the study participant experiences an irAE after the first infusion of cemiplimab/placebo at entry, study treatment should be discontinued (i.e., the participant would not receive the second infusion).

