#### 10.2.1 Primary Outcome Measures

##### 10.2.1.1 Safety

Occurrence of a Grade  $\geq 3$  AE, or Grade  $\geq 1$  irAE (such as, but not limited to, pneumonitis, colitis, adrenal insufficiency, or hypothyroidism), that is related to study treatment (as judged by the

core team, blinded to treatment arm) any time from study treatment administration through the week 48 visit.

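### Protocol 8.2.2 allows a restarted infusion to continue when the reaction recurs, but 8.2.3 defines recurrence after improvement as Grade 3 and requires a permanent stop: two incompatible actions, with a risk of misgrading

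*Protocol*

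**What the plan says.** Section 8.2 tells sites to grade infusion reactions by CTCAE version 5.0 and prints a definition and an action for each grade.

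- **8.2.1 (Grade 1).** The infusion is slowed by half. "If the infusion reaction recurs and/or persists at the decreased rate of infusion, the rate of the infusion may be further reduced".
- **8.2.2 (Grade 2).** The infusion is stopped. At the investigator's discretion, "the infusion may be continued at 50% of the previous infusion rate once the adverse reaction has resolved or has decreased to Grade 1". Then: "If the infusion reaction recurs at this rate of infusion, the rate may be further reduced, again at the discretion of the site investigator". Completion under monitoring is allowed.
- **8.2.3 (Grade 3).** The definition has alternatives joined by the word or. One is "recurrence of symptoms following initial improvement or hospitalization indicated for clinical sequelae". The action is immediate discontinuation, disconnection and no further study drug.
- **8.2, general text on Grades 3 and 4.** "The infusion should not be restarted and no further study medication (cemiplimab/placebo) should be given".
- **9.1.** Study treatment ends if "A Grade 3 or 4 infusion reaction occurs".

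The grade is used again in section 10. The primary safety outcome (10.2.1.1) counts a related AE of Grade 3 or higher. Escalation criterion A (10.4.1) and pause rule (a) (10.5) are each triggered by three participants with such an event. Efficacy analyses (10.6.2) use only participants who completed at least 90% of both infusions.

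**The concern.** Section 8.2.2 permits a restart only after the reaction has resolved or dropped to Grade 1. That is an initial improvement in the sense of 8.2.3, so every recurrence that 8.2.2 provides for also fits the printed Grade 3 definition. One section lets the infusion go on more slowly; the other ends it, together with all further study drug.

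The immediate stake is at the bedside, in participants for whom the protocol expects no direct benefit. The statistical stake follows from the action taken. Stopping removes infusion 2 if it is still due, and takes the participant out of the efficacy set unless at least 90% of both infusions had already been given. Continuing leaves both open.

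A second stake is the recorded grade. A site working under the Grade 2 heading may keep Grade 2 on the eCRF when the reaction recurs. If the event is related, it would then be left out of the Grade 3 part of the primary outcome, criterion A and pause rule (a).

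**Working it through.** **Step 1. The passages side by side.**

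| Event during infusion | 8.2.1 / 8.2.2 | 8.2.3, 8.2 and 9.1 |
|---|---|---|
| Grade 2 reaction resolves or falls to Grade 1, restart at half rate, reaction recurs | Rate may be lowered again; infusion may be completed | Recurrence after improvement is Grade 3: stop, no restart, no further drug |
| Grade 1 reaction improves at the lower rate, then recurs | Rate may be lowered again | Same Grade 3 wording |
| Grade 1 reaction persists without improving | Rate may be lowered again | Recurrence criterion not met; no conflict on this ground |

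The first row is a full conflict, the second applies only if there was improvement first, and the third is none. No sentence exempts recurrence at a reduced rate or gives one section precedence.

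**Step 2. What depends on the action.** If the infusion is stopped for good during infusion 1, infusion 2 is not given and the 90% condition in 10.6.2 fails. If it is stopped during infusion 2, the condition fails unless 90% had already run in. If the infusion continues and is completed, the condition can still be met.

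**Step 3. What depends on the grade.** The inputs are 12 active participants per cohort (10.4) and a related event.

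- Effect of one case on an arm's primary-outcome rate: 1/12 = 8.3 percentage points.
- Criterion A and pause rule (a) need three participants. A single regrading changes either only when two others already count.
- Infusion reactions are excluded from criterion B and pause rule (b), so a reaction below Grade 4 can reach these rules only through criterion A or rule (a), at Grade 3.

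**Step 4. Illustration for escalation.** The rule simulated in 10.4.1 is: escalate if, among 12 participants, there is no type C event, at most two have type A and at most one has type B. The check row is A = 0.03, B = 0.02, C = 0.01. The protocol does not state how A and B overlap, so the shared part was varied from 0 to 90% of the smaller rate. The result is 0.862 to 0.864 or 0.865, against the printed 0.86, so the plan's figure is reproduced.

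The protocol gives no rate of recurring reactions. Let q be an assumed rate of reactions that count as related Grade 3 events only if the 8.2.3 definition is applied. The chance of at least one among 12 is 1 − (1 − q)^12.

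| Assumed q | At least one of 12 | Escalation probability |
|---|---|---|
| 0 | 0 | 0.86 |
| 0.5% | 1 − 0.995^12 = 0.06 | 0.86 |
| 1% | 1 − 0.99^12 = 0.11 | 0.86 |
| 2% | 1 − 0.98^12 = 0.22 | 0.85 |

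At q = 2% the type A rate becomes 1 − 0.97 × 0.98 = 0.049, so this is no longer the 0.03 row. The table shows a direction and an order of size, not an error in the printed figure.

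**The case against.** **There is only one grading instrument.** Section 8.2 sends every infusion reaction to CTCAE, and the printed definitions mention recurrence only under Grade 3. The sentences in 8.2.1 and 8.2.2 direct management and assign no grade. A reader might infer that the protocol itself gives one event two grades and so two primary-outcome results. The text does not support that: a site that grades as instructed records Grade 3. This part of the objection stands. What remains is the conflict over action, and a risk of misgrading because 8.2.2 treats the recurrence under its Grade 2 heading.

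**Section 8 is guidance.** Section 8.0 says so and leaves room for clinical judgement, and the 8.2.2 sentence is permissive. But 8.0 also says that discontinuation criteria are mandated for toxicities related to study drug, and 9.1 lists a Grade 3 infusion reaction among them. A permission to continue and a mandate to stop still collide.

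**Replacement.** A reader might infer that the grade also decides whether the participant is replaced. It does not on either path. If the infusion is completed there is nothing to replace; if it is stopped for a related Grade 3 event, the safety endpoint has been reached and 6.2.5 and 10.4 exempt the participant.

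**Frequency.** Section 2.2 lists the treatment-related events above 5% among 757 oncology patients, and infusion reaction is not one of them, although its symptoms may be coded separately and the population differs. Recurrences are a subset of reactions. A large effect on escalation therefore has no support in the document.

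**Safeguards.** Grade 2 or higher infusion reactions go to the core team within 24 hours, and an unblinded SMC reviews escalation. These make it likelier that a misgraded case is noticed afterwards; they do not tell staff what to do during the infusion.

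**AESI wording.** Section 7.2 could be read as placing Grade 2 infusion reactions among irAEs, in which case a related Grade 2 reaction would already meet the primary outcome. Section 8.1 lists the two separately, and 10.4.1B and 10.5(b) exclude infusion reactions from their irAE counts. Even on that reading, criterion A, pause rule (a) and the stop rule still depend on the grade.

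**Conclusion.** The contradiction is established from the text alone: for a reaction that improves and then recurs at the reduced rate, 8.2.2 permits continuation, while 8.2, 8.2.3 and 9.1 require a permanent stop. Section 8.2.1 shares the problem only where a Grade 1 reaction improves before recurring. The firm consequence concerns the action, and through it infusion 2 and membership of the efficacy set.

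The effect on 10.2.1.1, 10.4.1A and 10.5(a) is conditional. It needs a site to record Grade 2 despite the printed definition, and the core team to judge the event related. Each such case would move an arm's rate by 8.3 percentage points. The effect on escalation is illustrative and small: about one percentage point at an assumed 2% recurrence rate. The point merits correction because it leaves staff with incompatible instructions, not because it would shift the operating characteristics much. No view is taken on which clinical rule is right.

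**What to change.** Reconcile the recurrence sentences in 8.2.1 and 8.2.2 with the Grade 3 definition in 8.2.3, so that a reaction recurring after initial improvement has one stated grade and one stated action. The clinical team should choose both. Add to 8.2 that this grade is the one entered on the eCRF and used in 9.1, 10.2.1.1, 10.4.1A and 10.5(a).

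The cost is a sentence or two in a protocol letter or amendment and a memo to sites. No additional data, visits or sample size are needed, and Table 10.4.1-1 can stay as printed.

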8.2.4 Grade 4: Life-threatening consequences; urgent intervention indicated

DISCONTINUE further doses of cemiplimab/placebo.

Participants who develop a Grade 4 AE or toxicity during a cemiplimab/placebo infusion should have infusion discontinued immediately and be disconnected from the infusion tubing. Administer epinephrine, corticosteroids, IV antihistamines, bronchodilators, and/or supplemental oxygen as medically indicated. No further study drug treatment should be administered. The core study team must be notified within 24 hours by email at [[contact]](mailto:[contact]).

## 8.3 Other Potential AEs/Toxicity

### 8.3.1 Diarrhea or Colitis

Diarrhea, blood, or mucus in stool, and/or abdominal pain

A high index of suspicion for immune-related colitis should be maintained in participants who present with diarrhea or other abdominal symptoms. The core study team must be notified immediately of all suspected cases of immune-related colitis by email at [[contact]](mailto:[contact]).

For any suspected or defined immune-related colitis diagnosed following cemiplimab/placebo infusion, further doses of the study drug MUST BE WITHHELD until the etiology of the colitis is evaluated and determined.

If there is evidence or history supporting a non-cemiplimab/placebo-related cause, documentation of this evidence and treatment of the non-cemiplimab/placebo-related cause should proceed. Routine, comprehensive medical assessment of diarrheal illness should be considered including stool culture, *C. difficile* testing as well as appropriate testing for ova and parasites, if indicated.

If there is no evidence of a non-cemiplimab-related cause, then manage diarrhea or colitis as per grade of severity (DAIDS, corrected version 2.1) as follows:

8.3.1.1 Grade 1: Transient or intermittent episodes of unformed stools OR increase of ≤three stools over baseline per 24-hour period

Participants who develop Grade 1 diarrhea should be treated symptomatically with medically indicated anti-diarrheal agents but without systemic steroids. Participants will continue study procedures as per protocol. Routine, comprehensive medical assessment of diarrheal illness should be considered including stool culture, *C. difficile* testing as well as appropriate testing for parasitic infestation with ova and parasite (O&P) diagnostic studies, if indicated. If above diagnostic tests are negative and diarrhea persists for 3 days, then obtain flexible sigmoidoscopy and biopsy to evaluate for immune mediated colitis. If there is an alternative diagnosis and/or symptoms resolve and the participant has not been diagnosed with immune-related colitis, then cemiplimab/placebo administration can proceed.

8.3.1.2 Grade 2: Persistent episodes of unformed to watery stools OR increase of four to six stools over baseline per 24-hour period

WITHHOLD further doses of cemiplimab/placebo.

Participants who develop Grade 2 diarrhea should be treated symptomatically with medically indicated anti-diarrheal agents but without systemic steroids and continue study procedures as per protocol. If symptoms worsen or do not improve to Grade ≤1 within 1 week, the following should be completed immediately:

- Stool WBC
- Stool culture
- *Clostridium difficile* toxin
- Stool O&P (if indicated)

The core study team must be notified within 24 hours by email at [[contact]](mailto:[contact]).

If stool studies reveal an infectious cause, specific treatment for the infection should be started. If stool studies are negative and/or inconclusive and Grade 2 symptoms persist, obtain endoscopic studies and/or abdominal CT scan. If colitis is observed per any diagnostic modality or clinically suspected, treatment with systemic corticosteroids should be started (recommended: prednisone 60 mg/day orally or methylprednisolone 0.5-1 mg/kg/day IV). Discussion with the A5370 study team prior to performing gastrointestinal biopsy and/or institution of systemic steroid therapy is strongly recommended.

If symptoms do not improve or worsen within 3 days of initiating steroids, obtain appropriate gastrointestinal or immunologic clinical consultation and consider use of high-dose steroids (recommended methylprednisolone 1-2 mg/kg/day IV) and taper over 4-6 weeks. Discussion with the A5370 study team prior to starting higher doses of steroid therapy is strongly recommended. Participants may continue study procedures unless clinically contraindicated.

8.3.1.3 Grade 3: Increase of  $\geq$ seven stools per 24-hour period OR IV fluid replacement indicated

WITHHOLD further doses of cemiplimab/placebo.

Participants who develop Grade 3 diarrhea should have the following diagnostic evaluations completed immediately:

- Stool WBC
- Stool culture
- *Clostridium difficile* toxin
- Endoscopy or abdominal CT scan

The core team must be notified within 24 hours by email at: [[contact]](mailto:[contact]).

If stool studies reveal an infectious cause, treatment for the specific infection should be started. If colitis is observed per endoscopy or abdominal CT scan or highly clinically suspected and infectious disease work-up is negative, appropriate subspecialty clinical consultation should be obtained. Discussion with the A5370 study team prior to biopsy or institution of systemic steroid therapy is strongly recommended. Consider systemic corticosteroids (recommend: methylprednisolone 1-2 mg/kg/day IV for 3 days then reduced to 1 mg/kg/day and taper over at least 1 month [59]). Participants may continue study procedures unless clinically contraindicated.

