#### Assessment Prior to Week 6 Cemiplimab/Placebo Administration

Prior to administering the second infusion at week 6 in all dose cohorts, the safety-related items in [sections 4.1](#) and [4.2](#) should be re-assessed by a site investigator or designee based on the week 4 evaluations (or the visit prior to the week 6 infusion, as appropriate). If the following are not confirmed, then the second infusion should not be given:

- Negative results for TPO antibody, GAD65/GAD antibody, and islet cell antibody.
- Negative or within normal range results for metabolic studies (fasting glucose, AM cortisol, TSH, and free T4).

These must be done at a laboratory that possesses a CLIA certification or equivalent.

Also, if any irAEs were identified following the first infusion or suspected irAEs are under investigation for relatedness, the second infusion must not be given.

NOTE A: If enrollment safety pause criteria are met (see [section 10.4.1](#)), participants already enrolled on study should not receive the second infusion pending SMC review, but should be followed for safety per NOTE B above. The study leadership will notify sites if and when a safety pause is needed and will also notify sites when the pause is lifted.

NOTE B: If enrollment is re-opened following SMC review, the above safety labs designated for week 4 should be repeated if collected >4 weeks prior to the rescheduled second infusion.

This information should be captured on the appropriate eCRF.

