NOTE C: The core team must be notified within 24 hours by email at [[contact]](mailto:[contact]) regarding any suspected or confirmed irAE of any grade that are considered to be related to study treatment. In such cases, cemiplimab/placebo should be withheld.

NOTE D: Should there be any question about whether an AE is considered an irAE, sites should withhold cemiplimab/placebo and immediately contact one of the protocol chairs (see contact information in [Protocol Team Roster](#) on page 6).

NOTE E: For toxicities that cause DISCONTINUATION of cemiplimab/placebo, future doses of cemiplimab/placebo should not be given to the participant. Whereas, for toxicities that cause WITHHOLDING of cemiplimab/placebo, there is potential for continued/future doses to be given once the toxicity(ies) in question have been further investigated by site investigator and the study core team.

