#### Guidelines for Management of Adverse Events of Special Interest (AESI)

All participants who receive treatment/placebo on this study should be closely monitored for any symptoms or signs related to irAEs including: gastrointestinal (colitis), endocrinopathies (hypo- and hyperthyroidism, adrenal insufficiency, hypophysitis, diabetes), symptoms or signs suggestive of pneumonitis, myocarditis, hepatitis, uveitis, dermatitis, or other irAEs. Such participants must be carefully followed, and managed at the first onset of these clinical symptoms. Sites should discuss any potential immune-related symptom with the A5370 core study team. For example, a high index of

suspicion for immune-related colitis should be maintained in participants who present with diarrhea or other abdominal symptoms, and a high index of suspicion for immune-related pneumonitis should be maintained in participants who present with respiratory symptoms.

Documentation of the immunopathologic nature of a suspected irAE by biopsy confirmation should be considered if there is no other clear cause, and/or when symptoms are severe or persistent. Discussion with the A5370 core study team prior to biopsy or institution of steroid therapy is strongly recommended if feasible. Prompt initiation of appropriate therapy should be instituted as outlined in the specific toxicity sections of the protocol ([sections 8.1-8.6](#)). Additional information is in the IB and a copy of the most current version of the IB should be readily available to study and other medical personnel following study participants.

Infusions of cemiplimab/placebo should be held in any participant who develops a suspected irAE regardless of grade. If the suspected irAE is confirmed as an irAE of any grade OR if the suspected irAE cannot be excluded, infusions should be discontinued. If, however, the AE is attributed to another cause, then infusions can be continued.

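### Section 8.3.1.1 allows dose 2 once suspected immune-related Grade 1 diarrhea resolves unexplained; section 8.0 says to stop treatment in the same case

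*Protocol*

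**What the plan says.** Three pieces of protocol text bear on the decision to give dose 2 after Grade 1 diarrhea.

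- **Section 8.0, AESI guidance.** Infusions are held for a suspected irAE of any grade. They stop if it is confirmed, "OR if the suspected irAE cannot be excluded, infusions should be discontinued". The one stated way back is: "If, however, the AE is attributed to another cause, then infusions can be continued".
- **Section 8.3.1, opening text.** For suspected or defined immune-related colitis, "further doses of the study drug MUST BE WITHHELD until the etiology of the colitis is evaluated and determined". The grade-specific rules are then reached as follows: "If there is no evidence of a non-cemiplimab-related cause, then manage diarrhea or colitis as per grade of severity".
- **Section 8.3.1.1, Grade 1.** Symptoms are treated with anti-diarrheal agents and stool work-up is to be considered. Endoscopy has its own trigger: "If above diagnostic tests are negative and diarrhea persists for 3 days, then obtain flexible sigmoidoscopy and biopsy to evaluate for immune mediated colitis". The release sentence follows: "If there is an alternative diagnosis and/or symptoms resolve and the participant has not been diagnosed with immune-related colitis, then cemiplimab/placebo administration can proceed".

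Section 6.3.5 adds a check before the week 6 infusion. It bars dose 2 if an irAE was identified after the first infusion or if "suspected irAEs are under investigation for relatedness, the second infusion must not be given".

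**The concern.** The release sentence in 8.3.1.1 joins its first two conditions with and/or, so resolution of symptoms satisfies it without any alternative diagnosis. Its remaining condition is that immune-related colitis has not been diagnosed. That is a weaker test than the one in 8.0, which asks whether the suspected event can be excluded. A condition nobody tested for is not diagnosed, but it has not been excluded either.

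At stake is re-exposure to a checkpoint inhibitor in otherwise healthy participants, for whom section 2.2 expects no direct benefit and relies on prompt discontinuation as a safeguard. Section 9.1 stops treatment for an irAE of any grade, so whether a suspected Grade 1 episode counts as excluded decides whether dose 2 is given. The escalation and pause criteria do not catch these cases: criterion B in section 10.4.1 counts colitis only from Grade 2. The individual dosing rule therefore carries the weight.

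**Working it through.** No plan figure is involved, so the check applies each rule to one defined case: Grade 1 diarrhea after dose 1, suspected to be immune-related, resolved, no cause found, no colitis diagnosis.

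1. **Does the case reach 8.3.1.1?** Yes. The grade rules apply when there is no evidence of a cause other than study drug. The resolution route therefore operates exactly where the way back in 8.0, attribution to another cause, is missing.
2. **Outcome under 8.3.1.1.** Symptoms have resolved and colitis was not diagnosed, so dose 2 is permitted.
3. **Outcome under 8.0.** The event was suspected, has not been attributed elsewhere and has not been excluded, so infusions should be discontinued.
4. **Outcome under the 8.3.1 opening text.** Doses stay withheld until a cause is determined. This is weaker support, because the sentence speaks of the cause of colitis, not of diarrhea in general.
5. **Could the release wording be met with no test for immune-related colitis?** Yes. Stool tests are only to be considered, and sigmoidoscopy with biopsy needs negative tests plus 3 days of persistence. An episode that settles sooner, possibly on the anti-diarrheal agents the section recommends, meets the wording untested. The wording also asks only about colitis, while the case definitions in 8.0 place immune-related diarrhea and colitis on one continuum.
6. **Does other text settle it?** The week 6 check in 6.3.5 covers identified irAEs and open investigations; it does not mention a suspected event that has resolved with no cause found. NOTE D in 8.0 says that when it is unclear whether an event is an irAE, "sites should withhold cemiplimab/placebo and immediately contact one of the protocol chairs", and NOTE E allows later dosing after joint investigation. Neither gives a criterion for release.

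Timing, for context only. The case definitions call onset of immune-related diarrhea/colitis at 4 to 6 weeks common. If that is counted from the first dose (an assumption):

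- onset: 4 × 7 = 28 to 6 × 7 = 42, so days 28 to 42
- dose 2: 42 ± 2, so days 40 to 44
- overlap: days 40 to 42

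This adds little. A suspected episode starting on days 40 to 42 would probably still be under investigation and so barred by 6.3.5. The cases that matter are earlier, brief ones, for which the protocol gives no rate.

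**The case against.** The strongest reply is that the rules have different triggers. Section 8.0 governs suspected irAEs; 8.3.1.1 speaks of Grade 1 diarrhea and, unlike Grades 2 and 3, has no instruction to withhold. On that reading 8.3.1.1 covers mild diarrhea, the stricter rules take over once suspicion forms, and a permission need not defeat a hold imposed elsewhere. This does not reconcile the texts. Saying that dosing can proceed presupposes a hold, and 8.3.1 asks for a high index of suspicion in anyone presenting with diarrhea.

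The second reply is that a site would not decide alone. Suspected colitis goes to the core team immediately, doubtful cases go to a protocol chair, and NOTE E makes investigation joint. This stands as a limit on exposure, but it settles who is consulted and not which rule governs release.

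Third, lighter handling at Grade 1 may be deliberate: section 2.2 names low-grade diarrhea as a common event, criterion B starts at Grade 2 for colitis, and section 8.0 calls its contents guidelines subject to clinical judgment. That supports leaving unsuspected Grade 1 diarrhea alone. It does not explain why a suspected case should meet two opposite instructions.

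Finally, frequency is unknown, and the primary outcome in 10.2.1.1 is still judged by the blinded core team whether or not dose 2 is given. Both points are correct and keep the finding modest.

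**Conclusion.** The concern holds. For suspected immune-related Grade 1 diarrhea that resolves unexplained, 8.3.1.1 and 8.0 give opposite dosing decisions, and no text sets their precedence. A site that discontinues breaches neither rule, since 8.3.1.1 only permits dosing; the defect is that a site that re-doses can also cite the protocol.

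At most one infusion per affected participant is involved. Frequency cannot be derived: the protocol gives no rate for Grade 1 diarrhea alone, for onset before week 6, or for episodes that resolve without a cause.

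The conclusion assumes that an irAE was actually suspected and that resolution does not by itself amount to exclusion; no passage says that it does. It should be corrected, as a narrow safety inconsistency and not a threat to the trial's analysis.

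**What to change.** Amend the last sentence of 8.3.1.1 along these lines: once an irAE has been suspected, the second infusion is given only if the site investigator and core team attribute the episode to another cause or document that an irAE has been excluded; resolution of symptoms alone does not suffice. Grade 1 diarrhea never suspected to be immune-related stays under the present rule. What evidence excludes an irAE in an episode already over would remain a joint clinical judgment, but the decision and its basis would be recorded.

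The cost is one sentence and a clarification to sites; the joint review already exists in NOTE E of 8.0. The downside is that a few participants with mild self-limited diarrhea may lose dose 2. They would be replaced under 6.2.5 and 10.4 unless the event is judged a primary safety endpoint. Since 10.6.2 restricts efficacy analyses to those completing at least 90% of both infusions, anyone not replaced would also be lost to those analyses.
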